After randomization for this study was complete, an additional endpoint to assess Worst Skin Pain response was included in the sequential testing procedure. This additional endpoint is based on the threshold for clinically meaningful change and is defined as at least a 3 point decrease from Baseline in HSSDD weekly worst skin pain score at Week 16 among study participants with a score of ≥ 3 at Baseline. Note that the power calculations reported in Table 2-1 for this endpoint are based on the sample size that was initially driven by the Worst Pain CFB endpoint as described above. With a 2-sided significance level of 0.025, the sample size of 104:52 in the subset of participants reporting Baseline HSSDD worst skin pain score at or beyond the threshold for clinically meaningful change (ie, Baseline HSSDD ≥ 3) provides 53% power for

detecting a statistically significant difference between bimekizumab Q4W and placebo in the proportion of Worst Pain responders.

Note that the power at the 0.025 level of significance associated with this endpoint for the comparison between bimekizumab Q2W and placebo is 95%. The Q4W comparison of Worst Skin Pain response vs placebo against the 0.05 level of significance is therefore likely, and the power at this significance level is 65%. Given the strength of the power for the bimekizumab Q2W arm vs placebo across endpoints, it is considered acceptable to have a relatively low power for this final endpoint in the testing sequence for the bimekizumab Q4W treatment arm vs placebo.

Table 2-1: Power calculation assumptions and methods

Endpoint	Power $\alpha = 0.025$, 2-sided		Assumptions		
	Q2W	Q4W	Week 16 Bimekizumab Q2W N=280 ^a	Week 16 Bimekizumab Q4W N=140	Week 16 Placebo N=70
HiSCR ₅₀	0.99	0.90	Proportion responders=0.60	Proportion responders=0.50	Proportion responders=0.25
HiSCR ₇₅	0.99	0.98	Proportion responders=0.45	Proportion responders=0.35	Proportion responders=0.10
DLQI	0.99	0.96	Mean CFB=-5.4; SD=6.8	Mean CFB=-4.8; SD=6.8	Mean CFB=-0.8; SD=6.6
Worst Skin Pain CFB ^b	0.89	0.73	Mean CFB=-2.2; SD=3.2	Mean CFB=-2.0; SD=3.2	Mean CFB=-0.5; SD=3.7
Worst Skin Pain Response ^c	0.95	0.53	Proportion responders=0.53	Proportion responders=0.43	Proportion responders=0.23

CFB=change from Baseline; Q2W=every 2 weeks; Q4W=every 4 weeks; SD=standard deviation

Note: Estimates for HS0003 are based on Week 12 data from the HS0001 study.

^a Pooled Q2W at Week 16 from Q2W/Q2W and Q2W/Q4W arms

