3. Estimates of the adjusted responder rate for each treatment group and the associated SE are obtained from the logistic regression of each of the 100 imputed data sets. These estimates will be combined for overall inference using Rubin’s rules, which account for the uncertainty associated with the imputed values (Rubin, 1987), and the combined estimates and SEs will be used to construct 95% CIs using the logit scale. This will be done using SAS PROC MIANALYZE. The combined estimates and 95% CIs on the logit scale will be back-transformed using the inverse logit link function to obtain the adjusted responder rates (%) and associated 95% CIs.

Note: The (unadjusted) proportion of responders will be calculated at each time point by treatment group from the imputed datasets using SAS PROC FREQ. These results will also be combined into an overall inference using SAS PROC MIANALYZE.

Some key points to consider relative to the calculation of the odds ratios and corresponding confidence intervals are noted below:

As the estimates of the odds ratios from the logistic regression models in Step 3 follow a log-normal distribution, a log transformation is needed to normalize these 100 odds ratio estimates. That is because the procedures for combining results from multiple imputed datasets assume that the statistics estimated from each imputed dataset are normally distributed. Therefore, the log of the odds ratio estimates from the logistic regression model are used when combining into a single inference (Step 3). Additionally, the SE for the odds ratios are transformed as follows:

$$SE = \frac{\log(UCL) - \log(LCL)}{2Z_{\alpha/2}}$$

Where UCL and LCL are the upper and lower confidence limit, respectively, for the CI of the odds ratio from the logistic regression model, and $Z_{\alpha/2}$ is the relevant critical value from the standard normal distribution (2.24 for a 97.5% CI). The estimates of the log odds ratio for Bimekizumab relative to placebo and the corresponding upper and lower CLs will be provided. The odds ratio will be then estimated by exponentiating the estimate of the log odds ratio. The odds ratio and the confidence limits of the odds ratio will be estimated as follows:

$$OR = \exp(\text{Log odds ratio estimate})$$

$$LCL = OR * \exp(-SE * Z_{\alpha/2})$$

$$UCL = OR * \exp(SE * Z_{\alpha/2})$$

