Where OR is the back-transformed estimate of the odds ratio just described, SE is the SE of the log odds ratio and $Z_{\alpha/2}$ is the relevant critical value from the standard normal distribution (2.24 for a 97.5% CI). These calculations will be done such that odds ratios and corresponding CIs are calculated for the odds ratio of bimekizumab vs. placebo.

Note: If one dose regimen is tested at the 0.05 significance level as determined in Section 4.5, then the confidence interval will be 95% instead of 97.5% for that dose with a corresponding $Z_{\alpha/2}$ of 1.96.

In addition to calculating the odds ratio, associated CIs, and p-values for the pairwise comparisons of bimekizumab and placebo, the estimated proportion of responders (ie, estimated responder rate) and the difference in the proportion of responders between each bimekizumab treatment group and placebo will be estimated, and 2-sided 95% CIs will be created for each difference. The creation of the estimates of the differences will be completed for each bimekizumab treatment group using the process detailed below:

1. Use the logistic regression model to calculate:

Least squares mean estimates of the log odds of bimekizumab (G_B) and placebo (G_P), as well as their corresponding standard errors (S_B and S_P , respectively).

Standard error of the least squares mean estimate of the log odds ratio (S_R)

2. Compute estimates for predicted proportions using the following transformations:

$$P_B = \exp(G_B) / (1 + \exp(G_B))$$

$$P_P = \exp(G_P) / (1 + \exp(G_P))$$

The difference in proportions is then given by:

$$D = P_B - P_P$$

3. Estimate the standard error of D by:

$$S_D = \sqrt{[P_B^2(1-P_B)^2S_B^2 + P_P^2(1-P_P)^2S_P^2 + P_B(1-P_B)P_P(1-P_P)S_R^2 - P_B(1-P_B)P_P(1-P_P)(S_B^2 + S_P^2)]}$$

The MCMC method for multiple imputation, as previously outlined, will be used to account for missing values. The calculation steps described above will be based on the results provided from the logistic regression model of the multiple imputed datasets. An estimate for the difference in proportions, D, and corresponding standard error, SD, will be computed for each of these datasets. The results from these analyses will be combined into a single estimate of the difference in predicted proportion of response and a 2-sided 95% CI interval using SAS PROC MIANALYZE.

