4.8 Examination of subgroups

Subgroup analyses will be performed on the HiSCR₅₀, HiSCR₇₅, and worst skin pain response endpoints by visit for the Initial Treatment Period and Maintenance Treatment Period. Additional subgroup analyses will be performed on the CFB in the worst skin pain score as measured by HSSDD and in the DLQI total score through Week 16 as described below.

Along with the tables described, there will be tables for HiSCR₅₀, HiSCR₇₅, and skin pain response endpoints which display the response difference and 95% CIs between each bimekizumab dose regimen versus placebo for each of the subgroups at Week 16. Corresponding forest plots will be prepared.

The following subgroup variables will be determined using Baseline data, except for analgesic use, lesion intervention, and antibody positivity:

- Age (<40 years, 40 to <65 years, \geq 65 years)
- Gender (male, female)
- Disease duration (<median, \geq median)

The median disease duration will be calculated based on all participants in the analysis set used for analysis.

- Region (North America [Canada, USA], Western Europe [Belgium, France, Germany, Italy, Norway, Spain, Switzerland, Denmark, Netherlands], Central/Eastern Europe [Greece], Asia/Australia [Australia, Israel, Turkey])
- Weight (\leq 100 kg, >100 kg)
- BMI (<25 kg/m², 25 to <30 kg/m², \geq 30 kg/m²)
- Race (Black or African American, White, All Other Races [American Indian or Alaska Native, Asian, Native Hawaiian or Other Pacific Islander, Other/Mixed])
- Systemic antibiotic therapy at randomization (yes, no)
- Prior biologic therapy for any indication (yes, no)
- Prior biologic therapy for HS (yes, no)
- Hurley Stage at Baseline (II or III)
- Analgesic users (yes, no), separately for the Initial Treatment Period and the Maintenance Treatment Period (Section 6.4.2 specifies how participants are classified as analgesic users)
- Lesion intervention (yes, no), separately for the Initial Treatment Period and the Maintenance Treatment Period

- Antibody positivity (confirmatory assay: negative or positive; see Section 9.3.2)
- Antihistamine users during the Initial Treatment Period (yes, no) (Section 6.4.2 specifies how participants are classified as antihistamine users) (applicable only to the skin pain response endpoint)

The following subgroups for analysis on the CFB in the worst skin pain score as measured by HSSDD and in the DLQI total score will be determined based on medication use during the Initial Treatment Period:

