8.2.2 Primary analysis of the primary efficacy endpoint

The primary endpoint is the HiSCR₅₀ response at Week 16 and corresponding analyses are based on the RS. The primary efficacy analysis will evaluate the composite estimand in the RS as described in Table 8-1. The composite estimand combines the clinically meaningful improvement from Baseline based on the HiSCR₅₀ response and completion of study treatment through Week 16 without receiving systemic antibiotic rescue medication or discontinuing IMP due to an AE or lack of efficacy.

The following 4 attributes describe the estimand that will be used to define the treatment effect of interest for the primary efficacy analysis:

1. Population=Study participants meeting the protocol-specified inclusion/exclusion criteria.
2. Study participant-level outcome=HiSCR₅₀ at Week 16.
3. Intercurrent event handling=An intercurrent event is defined as receipt of systemic antibiotic rescue medication or discontinuation of study treatment due to an AE or lack of efficacy prior to Week 16. More information is provided in Section 3.9. A composite strategy will be implemented in which a positive clinical outcome is defined as achieving HiSCR₅₀ at Week 16 and not receiving systemic antibiotic rescue medication, and not discontinuing study treatment due to an AE or lack of efficacy through Week 16. Any missing data at Week 16 that are not preceded by an intercurrent event will be imputed using multiple imputation as defined in Section 4.2.1. The rationale for this composite estimand is provided in Section 4.2.3.1.

4. Population-level summary measure=conditional odds ratio comparing bimekizumab to placebo adjusted for stratification factors used in the randomization.

The statistical hypothesis for the HiSCR₅₀ response at Week 16 is that the conditional odds ratio for the HiSCR₅₀ response in the bimekizumab treatment group relative to the placebo group is equal to 1.

The primary analysis will be based on a logistic regression model including a fixed effect for treatment, Hurley stage at Baseline, and Baseline antibiotic use. The odds ratio versus placebo, p-value (from Wald test), and 97.5% CI will be calculated. If one dose regimen is tested at the 0.05 significance level as determined in Section 4.5, then the confidence interval will be 95% instead of 97.5% for that dose with a corresponding $Z_{\alpha/2}$ of 1.96.

The number and percentage of participants who are HiSCR₅₀ responders at Week 16 will be summarized.

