8.5 Additional statistical analyses of other efficacy endpoints

For selected other efficacy variables, it is of interest to perform statistical tests and to calculate inferential statistics. As these tests are not part of the multiplicity-controlled procedure, the associated p-values are considered nominal and are not controlled for multiplicity.

For binary variables, the analysis will follow what was specified for the primary analysis of the primary endpoint and the corresponding p-value reported. Missing values will be imputed as for the primary analysis. For continuous variables, the MI – MCMC / Monotone Regression approach used for the secondary continuous endpoint will be applied for the imputation model. The analysis model will be as for the corresponding secondary continuous endpoint analysis, unless otherwise indicated.

Below is a list of variables for which these nominal p-values will be calculated. The results of these inferential tests will be presented in a single table summarizing the testing performed outside of the multiplicity-controlled testing procedure.

All tests will be for both 320mg Q2W vs Placebo and 320mg Q4W vs Placebo (tested separately) and will be performed for the Week 12 and Week 16 visits only. If the Week 16 visit test is already part of the controlled testing procedure in the primary or secondary analyses, only Week 12 is indicated here.

- HiSCR₅₀ at Week 12
- HiSCR₇₅ at Week 12
- HiSCR₉₀
- HiSCR₁₀₀
- Flare by Week 12
- Flare by Week 16
- Time to flare by Week 12 (based on time-to-event analysis per Section 8.4.5 and adjusted appropriately)
- IHS4 change from Baseline
- IHS4 percentage change from Baseline
- HS Physician's Global Assessment: rate of participants who are Clear or Mild
- DLQI total score change from Baseline at Week 12
- Worst Skin Pain per HSSDD change from Baseline at Week 12
- Skin Pain response per HSSDD at Week 12

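### The nominal HiSCR90 and HiSCR100 tests use a Wald logistic p-value that breaks down if no placebo participant responds, and the SAP names no fallback

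*SAP*

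**What the plan says.** The rule for these endpoints is built from four places in the SAP.

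- **Section 8.5** lists HiSCR90 and HiSCR100 for inferential testing, each dose against placebo. It says: "For binary variables, the analysis will follow what was specified for the primary analysis of the primary endpoint and the corresponding p-value reported". The tests "will be performed for the Week 12 and Week 16 visits only", and "the associated p-values are considered nominal and are not controlled for multiplicity".
- **Section 8.2.2** defines that primary analysis as "based on a logistic regression model including a fixed effect for treatment, Hurley stage at Baseline, and Baseline antibiotic use", with a Wald p-value.
- **Section 4.2.2.1** fits the model in each of 100 imputed data sets and pools on the log odds ratio scale by Rubin's rules. The stated reason begins: "As the estimates of the odds ratios from the logistic regression models in Step 3 follow a log-normal distribution". The standard error is recovered from the logs of the two confidence limits.
- **Section 2.4** puts 70 participants on placebo. Table 2-1 assumes a placebo HiSCR75 rate of 10% ("Proportion responders=0.10"), and gives no rate for HiSCR90 or HiSCR100.

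The convergence provisions in 4.2.2.1 concern the imputation model. Those in 8.2.3.11 concern the center-by-treatment model. The CMH test in 8.2.3.10 is planned for the primary endpoint only. Nothing covers an outcome model in which one arm has no responder.

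**The concern.** By the definitions in 8.4.1.1, every HiSCR90 or HiSCR100 responder is also a HiSCR75 responder. The placebo rates for the two stricter endpoints therefore cannot exceed the HiSCR75 rate, assumed to be 10%. With 70 placebo participants, and intercurrent events counted as nonresponse, a placebo arm with no responder is a realistic outcome.

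In such a data set the likelihood keeps rising as the log odds ratio grows. The software stops at some large estimate with a very large standard error, and the Wald ratio shrinks towards zero. Both doses share the placebo arm, so both comparisons fail together. Rubin's within-imputation variance is the average of the squared standard errors, so one such set can dominate the pooled result.

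At stake is the table of nominal results. It could show a p-value near 1 next to response rates of 0% and 15%, and any substitute test would then have to be chosen after unblinding.

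**Working it through.** **Inputs.** From the SAP: 280 (pooled Q2W), 140 (Q4W) and 70 (placebo) participants; HiSCR75 rates of 35% on Q4W and 10% on placebo; two-sided alpha 0.025; 100 imputations. Assumed: active counts of 42/280 (15%) and 18/140 (13%), the split of the two stratification factors, and placebo rates of 1% to 5%.

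**1. The plan's own figure.** Power for HiSCR75, Q4W versus placebo:

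- Pooled rate (49 + 7)/210 = 0.267, so the null SE = √(0.267 × 0.733 × (1/140 + 1/70)) = 0.0647.
- Alternative SE = √(0.35 × 0.65/140 + 0.10 × 0.90/70) = 0.0540.
- z = (0.25 − 2.24 × 0.0647)/0.0540 = 1.94, so power = 0.974. The SAP states 0.98; the setting is reproduced.

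**2. Chance of no placebo responder**, (1 − p)^70: 49% at p = 1%, 24% at 2%, 12% at 3%, 3% at 5%, and 0.06% at 10%.

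**3. The planned test with 0/70 on placebo** (three arms, two binary covariates):

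| Stop at iteration | Log OR, Q2W | SE | Wald p, Q2W | Wald p, Q4W |
|---|---|---|---|---|
| 8 | 7.39 | 11.9 | 0.53 | 0.54 |
| 12 | 11.39 | 87.6 | 0.90 | 0.90 |
| 15 | 14.39 | 392.7 | 0.97 | 0.97 |
| 18 | 17.39 | 1760 | 0.992 | 0.992 |
| 25 | 24.39 | 58261 | >0.999 | >0.999 |

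Active rates between 8% and 20% give nearly the same p-values. The standard-error recipe in 4.2.2.1 also fails. At iteration 15 the limits are exp(14.4 ± 2.24 × 392.7), about exp(894) and exp(−865), which overflow and underflow in double precision.

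**4. One separated set in 100.** If all 100 sets contain one placebo responder, the pooled Q2W log OR is 2.43 with SE 1.02, p = 0.017 (Q4W: p = 0.031). Replace one of them with a separated set stopped at iteration 15:

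- Within-imputation variance = (392.7² + 99 × 1.02²)/100 ≈ 1543.
- Between-imputation variance = (14.39 − 2.43)²/100 = 1.43.
- Pooled log OR 2.55, SE √(1543 + 1.01 × 1.43) = 39.3, p = 0.95.

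The same arithmetic gives p of about 0.13 for a stop at iteration 8, 0.78 at iteration 12 and above 0.999 at iteration 25.

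**5. Tests that tolerate a zero cell** (0/70 against 42/280, then 18/140):

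- Fisher: p = 0.00006 and 0.001.
- Unstratified CMH statistic, Q2W: expected responders on active 280 × 42/350 = 33.6, difference 8.4, variance 280 × 70 × 42 × 308/(350² × 349) = 5.93. So 8.4²/5.93 = 11.9, p = 0.0006. With the assumed strata, the stratified test gives 0.0005 (Q2W) and 0.002 (Q4W).
- Firth penalised likelihood-ratio test: p = 0.00009 and 0.0008.
- Firth fit read with a Wald p: 0.026 and 0.038.

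**6. The CMH test under pooling.** For 1/70 versus 42/280 the unstratified statistic is 7.6²/6.05 = 9.54. The Wilson-Hilferty transform, (Q^(1/3) − 7/9)/√(2/9), gives 2.85 for that set and 3.19 for the 0/70 set. One separated set among 99 others leaves the pooled value at 2.85, p = 0.002.

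**7. Subgroup differences (secondary).** Section 4.2.2.1 has a step headed "Estimate the standard error of D by". Every placebo term in that formula tends to zero as the placebo rate does. For an illustrative 12/20 versus 0/5, SE = √(0.6 × 0.4/20) = 0.110, so the 95% interval is 39 to 81 points. Newcombe's interval is 12 to 78.

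**The case against.** The strongest case against concerns reach and consequence, not the mechanism.

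- **No decision rests on these tests.** Section 3.10 says nominal p-values are not to be used to declare significance. This stands. A reader might infer that the confirmatory results are at risk, but the documents do not support that. At the assumed rates the chance of no placebo responder is 0.0006 for HiSCR75 (0.90^70) and about one in a million for skin pain response (0.77^52).
- **The trigger is conditional.** One observed placebo responder without an intercurrent event puts a responder in every imputed set, and the failure does not arise. This stands. The SAP gives no HiSCR90 or HiSCR100 rates, so one cannot say that it will happen.
- **No single wrong p-value follows.** A reader might take 0.9 to 0.99 as the planned result. The value depends on the stopping rule and can be nearer 0.5, or lower when only one of 100 sets is separated. That arbitrariness is the defect.
- **Other displays survive a zero cell.** Section 4.2.1.3 plans nonresponder-imputation and observed-case analyses of both endpoints. Section 3.1 specifies Wilson intervals for rates under nonresponder imputation. Section 8.4.1.2 plans stratified log-rank comparisons with placebo. These limit the harm but do not repair the 8.5 p-value.
- **The subgroup point is weaker.** Section 4.8 asks for tables that "display the response difference and 95% CIs between each bimekizumab dose regimen versus placebo for each of the subgroups at Week 16", but covers HiSCR50, HiSCR75 and skin pain response. It does not cite the standard error in 4.2.2.1 and limits output to descriptive statistics. The subgroup sizes above are illustrative. It holds only if that formula is the one used.

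**Conclusion.** The concern holds in limited form. As written, the SAP prescribes for HiSCR90 and HiSCR100 a test whose p-value becomes a computing artefact when no placebo participant responds, even where the data show a clear effect. In the worked example, with every set separated, it reports about 0.5 to above 0.99 where exact and CMH tests give 0.00006 and 0.0005. A single separated set in 100 takes the pooled Q2W p from 0.017 to 0.78 or more once fitting has run 12 or more iterations. The probability of the trigger rests on assumed placebo rates: 49% at 1%, falling to 3% at 5%. The active rates are also assumed, but the failure hardly depends on them. The damage is confined to nominal results, so this merits a short amendment before unblinding and does not threaten the trial's main conclusions.

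**What to change.** In 8.5, state that the nominal p-values for HiSCR90 and HiSCR100 come from the CMH test of 8.2.3.10, stratified by Hurley Stage and Baseline antibiotic use. Combine the statistics over the 100 imputations after a normalising transformation of the chi-square, such as Wilson-Hilferty, and write that step out. Report the odds ratio and interval from Firth-penalised logistic regression, pooled on the log scale. Apply both rules to these two endpoints regardless of the counts, so that nothing is triggered by the data. Do not take the p-value from a Firth Wald test.

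In 4.8, name the interval for subgroup response differences. Where placebo has no responder, use a score or Newcombe-type interval, and state how it is computed from imputed data.

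The cost is a few sentences and modest programming. The odds ratio is shrunk slightly, and its interval comes from a different method than the p-value, so the two can disagree near the threshold. A footnote should say so.

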For the purpose of the tabulations the lower and upper confidence limits for the percentages will be truncated at 0 and 100% respectively. Confidence intervals (CIs) for the response rates in efficacy summaries based on nonresponder imputation (NRI) will be computed using the Wilson approximation.

For bimekizumab PK concentrations, summary statistics will include geometric mean, geometric coefficient of variation (CV), 95% CIs for geometric mean, arithmetic mean, SD, median, minimum, and maximum. All summaries of PK variables will be based on the observed values. No imputation will be used.

Decimal places for descriptive statistics will be subject to the following rules:

- “n” will be an integer
- Mean, SD, and median will use 1 additional decimal place compared to the original data
- CV [%] will be presented with 1 decimal place
- Minimum and maximum will have the same number of decimal places as the original value.

Derived variables in general will display the mean, SD, and median to 1 more decimal place than the variables used in the derivation. If the number of decimal places reported in the raw data is varied then use either the maximum raw number of reported decimal places or 3, whichever is the lowest, as a guide for the descriptive statistics.

When reporting individual values and descriptive statistics for PK concentration data, the following rules will apply with regard to rounding and precision:

- Individual values will be reported to the same level of precision as received from the bioanalytical laboratory
- Descriptive statistics will be reported to the same level of precision as the individual data for the minimum and maximum, and to 1 additional significant figure for the mean (arithmetic and geometric), median, SD, and 95% CI for the geometric mean
- The geometric coefficient of variances (geoCV) will be reported as a percentage to 1 decimal place

Statistical tests of efficacy variables will be presented as 2-sided p-values rounded to 3 decimal places. P-values less than 0.001 will be presented as “<0.001” and p-values greater than 0.999 will be presented as “>0.999.” Statistical comparisons will be 2-sided and will be performed at the 0.05 level of significance unless specified otherwise. The significance levels used as part of the multiple testing procedure are detailed in Section 4.5.

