4.5 Multiple comparisons/multiplicity

To control the overall type I error rate at 0.05 for the multiple comparisons in the primary and secondary efficacy endpoints, a closed testing procedure under a parallel gatekeeping framework will be applied (Sun, 2018).

Under this framework, each bimekizumab dose of 320mg Q2W and 320mg Q4W will be compared to placebo in the first instance at a familywise error rate of 0.025 ($\alpha/2$). Simultaneously within each dose, closed testing for the primary and secondary efficacy endpoints will be performed as follows:

[figure not shown]
1. Step 1: Test HiSCR_{50} at significance level 0.025.
2. Steps 2 to 5 – If Step 1 is significant at 0.025 then test each secondary endpoint sequentially in the order shown in Figure 4-1, moving to the next step only if significance achieved at 0.025.
3. In the event that Step 5 is significant at 0.025 for a given dose, then Steps 1 to 5 will be repeated for the other dose using a significance level of 0.05.

The secondary efficacy variables supporting the primary efficacy variable are listed below, and will be included in the multiplicity adjustment using the analysis methods specified in Section 8.3:

1. Proportion of study participants who achieve HiSCR_{75} at Week 16.
 - a. bimekizumab 320mg Q2W vs placebo

- b. bimekizumab 320mg Q4W vs placebo
2. Absolute CFB in DLQI Total Score at Week 16.
 - a. bimekizumab 320mg Q2W vs placebo
 - b. bimekizumab 320mg Q4W vs placebo
3. Absolute CFB in Skin Pain Score at Week 16, as assessed by the “worst skin pain” item (11-point numeric rating scale) in the HSSDD.
 - a. bimekizumab 320mg Q2W vs placebo
 - b. bimekizumab 320mg Q4W vs placebo
4. Skin pain response at Week 16, based on the threshold for clinically meaningful change (defined as at least a 3 point decrease from Baseline in HSSDD weekly worst skin pain score) at Week 16 among study participants with a score of ≥ 3 at Baseline.
 - a. bimekizumab 320mg Q2W vs placebo
 - b. bimekizumab 320mg Q4W vs placebo

Figure 4-1: Sequence of testing

AN=abscess and inflammatory nodule; DLQI=Dermatology Life Quality Index; HiSCR₅₀=a 50% reduction in the total AN count with no increase from Baseline in abscess or draining tunnel count; HiSCR₇₅=a 75% reduction in the total AN count with no increase from Baseline in abscess or draining tunnel count; HS=hidradenitis Suppurativa; Q2W=every 2 weeks; Q4W=every 4 weeks

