- If Q7 is marked as "no" or "not relevant" and Q7a is missing, a score of 0 is given.
- If Q7 is missing and Q7a is missing, Q7 is considered unanswered (see below for details on how this impacts the DLQI total score).

If 1 question is left unanswered, this is scored 0 and the scores are summed and expressed as usual out of a maximum of 30. If 2 or more questions are left unanswered, the questionnaire is not scored.

Change from Baseline in DLQI total score is defined as Week 16 DLQI total score minus Baseline DLQI total score.

8.3.2.1 Primary analysis of change from Baseline in DLQI Total score at Week 16

Missing data imputation described in Section [4.2.1.2](#) will be applied.

Change from Baseline in DLQI total score will be presented by treatment group. The analysis model will be based on an ANCOVA with fixed effects of treatment, Hurley Stage at Baseline, Baseline antibiotic use and Baseline value as a covariate. The least square mean (LSM), standard error (SE), and 95% CI for the LSM will be presented by treatment group. For the comparison between placebo and bimekizumab: the difference between the LSM, the associated 97.5% CI for the contrasts, and the corresponding p-value will be presented. If one dose regimen is tested at the 0.05 significance level as determined in Section [4.5](#), then the confidence interval will be 95% instead of 97.5% for that dose with a corresponding $Z_{\alpha/2}$ of 1.96. Estimand and intercurrent event details are specified in [Table 8–2](#).

8.3.2.2 Sensitivity analysis of change from Baseline in DLQI Total score at Week 16

A sensitivity analysis using the same analysis model as in Section [8.3.2.1](#) will be used, based on observed data. Estimand and intercurrent event details are specified in [Table 8–2](#).

8.3.3 Change from Baseline in Skin Pain score at Week 16, as assessed by the “worst skin pain” item in the HSSDD

The items on the HSSDD assess patients' perception of the core symptoms of HS experienced in the past 24 hours: pain, smell or odor, drainage or oozing from HS lesions, and itch on an 11-point numeric rating scale (NRS). Two items assess skin pain: worst skin pain and average skin pain.

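### The responder-rate difference always gets a 95% interval, even for a dose tested at 0.025, so it can exclude zero beside a failed test and an odds-ratio interval that includes 1

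*SAP*

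**What the plan says.** Section 4.5 has each dose "compared to placebo in the first instance at a familywise error rate of 0.025". If one dose passes Step 5 at that level, "then Steps 1 to 5 will be repeated for the other dose using a significance level of 0.05". Section 3.1 makes all comparisons 2-sided.

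The interval levels for the contrasts in this hierarchy are:

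- **Odds ratio, binary endpoints.** Section 8.2.2: "The odds ratio versus placebo, p-value (from Wald test), and 97.5% CI will be calculated". Section 4.2.2.1 adds that if a dose is tested at 0.05, "then the confidence interval will be 95% instead of 97.5% for that dose with a corresponding $Z_{\alpha/2}$ of 1.96". Section 8.3.4.1 repeats the rule for skin pain response.
- **Mean difference, continuous endpoints.** Section 8.3.2.1 (DLQI): "the difference between the LSM, the associated 97.5% CI for the contrasts, and the corresponding p-value will be presented", with the same switch to 95% after recycling. Section 8.3.3.1 says the same for worst skin pain.
- **Responder-rate difference, binary endpoints.** Section 4.2.2.1, just after the note on switching levels: "and 2-sided 95% CIs will be created for each difference". The later step that pools the difference over imputations gives 95% again. Neither sentence refers to Section 4.5.

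The SAP marks other results as outside the controlled procedure: the Section 8.5 p-values are nominal and the Section 4.8 subgroup summaries are descriptive only. The Week 16 difference interval carries no such label.

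**The concern.** The odds ratio and the rate difference come from one logistic model and describe one comparison, yet for a dose still at 0.025 their intervals use different error levels. The table could then show a failed test and an odds-ratio interval covering 1 beside a rate difference whose interval lies wholly above 0. This touches Steps 1, 2 and 5 (HiSCR50, HiSCR75, skin pain response). Steps 3 and 4 (DLQI, worst skin pain change) have matched levels, and no reason is given for treating the two kinds of endpoint differently. The conflict appears only in borderline results, where choosing the interval afterwards would look data-driven.

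**Working it through.** **Inputs.** Section 2.4 and Table 2-1: Q2W 280 (pooled), Q4W 140, placebo 70; HiSCR50 rates 0.60, 0.50, 0.25; skin pain response 0.53, 0.43, 0.23 on 208, 104, 52. Section 4.2.2.1: critical values 2.24 (97.5%) and 1.96 (95%), and the formula for S_D. The calculations assume unstratified tables and no missing data.

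**The plan's own figures.** The 2-sided 0.025 normal quantile is 2.2414, against 2.24 stated. Normal-approximation power for Q4W HiSCR50 at 0.025 is 0.907, against 0.90 stated; for Q2W it is 0.9996, against 0.99. The inputs reproduce.

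**A single table: Q4W 54/140 (38.6%), placebo 17/70 (24.3%).**

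- Odds ratio = (54 × 53)/(86 × 17) = 1.958; log = 0.672.
- SE = √(1/54 + 1/86 + 1/17 + 1/53) = 0.328; z = 2.05; p = 0.041. The dose fails at 0.025.
- 97.5% CI for the odds ratio = exp(0.672 ± 2.24 × 0.328) = 0.938 to 4.085, which includes 1.
- D = 0.143. Without covariates S_D reduces to √(0.386 × 0.614/140 + 0.243 × 0.757/70) = 0.0657.
- 95% CI for D = 0.143 ± 1.96 × 0.0657 = 1.4 to 27.2 points, which excludes 0.
- 97.5% CI for D = 0.143 ± 2.24 × 0.0657 = −0.4 to 29.0 points, which agrees with the test.

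Pooled Q2W 104/280 against 17/70 behaves the same way: p = 0.045, odds-ratio CI 0.930 to 3.648, difference 95% CI 1.3 to 24.4 points. Every table examined with p between 0.025 and 0.05 showed the conflict.

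**How often, for a dose that stays at 0.025.** Exact binomial enumeration for Q4W HiSCR50, placebo rate 0.25, gives the chance that the test fails while the difference interval excludes 0:

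| True Q4W rate | Test fails | Conflict, 95% CI | Conflict, 97.5% CI |
|---|---|---|---|
| 0.50 (planned) | 9.5% | 4.8% | 1.5% |
| 0.45 | 27.3% | 11.3% | 3.9% |
| 0.40 | 54.3% | 16.5% | 6.2% |
| 0.25 (no effect) | 99.0% | 2.1% | 0.7% |

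For Q4W skin pain response at the planned rates, the 95% conflict figure is 15.9%.

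**Allowing for recycling.** Once Q2W clears all five steps, Q4W is tested at 0.05 and 95% is the matching level on both scales. Simulation at the Table 2-1 values, with a shared placebo arm and assumed endpoint correlations, puts that at about 87 to 88% of trials (86% at the low end). If the events were independent, the remaining 12 to 13% would give 4.8% × 0.12 to 0.13 ≈ 0.6% for HiSCR50 and 15.9% × 0.12 to 0.13 ≈ 1.9 to 2.1% for skin pain response. Simulating the events jointly gives about 0.5 to 1.4% and 1.2 to 2.0%. The spread reflects the assumed correlation and whether only p between 0.025 and 0.05 is counted or any failed test whose difference interval excludes 0. The skin pain figures do not require Q4W to have reached Step 5.

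**The case against.** Section 8.2.2 names one summary measure, the conditional odds ratio, with one hypothesis and one decision statistic. The rate difference is added to it; it has no hypothesis, no p-value and no place in Section 4.5. A conventional 95% level for a supplementary estimate is defensible, and the SAP uses it for within-arm rates and subgroup differences. This stands as a reason why no decision changes. It does not explain why the difference is unlabelled when the continuous contrasts are matched. The Amendment 1 log (Section 13.1, Changes #39 and #40) shows that the sponsor moved those contrasts from 95% to 97.5%.

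A reader might infer that the error rate is breached. With a dose correlation of (1/70)/√((1/70 + 1/280)(1/70 + 1/140)) = 0.73, the chance under the null that at least one of the two 95% difference intervals excludes 0 is about 0.082. The documents do not support that inference. The 0.05 in Section 4.5 belongs to the testing procedure, which uses the Wald p-value and never the difference interval. The 0.082 is the joint non-coverage of two unadjusted intervals.

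A reader might also take the gap between Q4W power at 0.05 and at 0.025 as the chance of conflict: about 4% for HiSCR50 (0.948 − 0.907) and 11% for skin pain response (0.700 − 0.588; the SAP's own 65% and 53% give 12%). That ignores recycling, which removes most of those cases.

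Finally, matching levels does not remove all disagreement, because a Wald test on the log odds and a delta-method difference are on different scales: 56/140 against 17/70 still gives an odds-ratio CI of 0.997 to 4.331 beside a 97.5% difference CI of 1.0 to 30.5 points. Nor does a level-matched interval show that an endpoint passed in sequence, since it may exclude the null after an earlier step has failed. Both points stand.

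**Conclusion.** The inconsistency is real and limited to reporting. For a dose tested at 0.025, the plan gives the rate difference a less strict level than the odds ratio and the continuous contrasts in the same hierarchy, without calling it descriptive. Type I error of the testing procedure is unaffected, and a dose promoted to 0.05 shows no mismatch. If the Table 2-1 assumptions hold, the conflict is rare: roughly 1% of trials for Q4W HiSCR50 and 1 to 2% for Q4W skin pain response. It becomes more likely if true effects fall short, because borderline results are then commoner and recycling less certain. These figures ignore stratification and multiple imputation and rest on assumed endpoint correlations.

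**What to change.** In both sentences of Section 4.2.2.1 that set the level for the difference in proportions (the introductory one and the pooling step), specify a 2-sided 97.5% CI, or a 95% CI for a dose tested at the 0.05 level per Section 4.5. Leave the within-arm responder-rate intervals at 95%. If a 95% difference interval is kept, label it as descriptive and not multiplicity-adjusted.

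The cost is a change to two sentences and one alpha setting in the program. When no alpha is recycled the difference interval becomes about 14% wider (2.24/1.96 = 1.14). A little discordance remains because of the two scales: for Q4W HiSCR50 at the planned rates and level 0.025, it falls from 4.8% to 1.5%.
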